**Table 31: ECG Change from Baseline by Parameter, Dose Group, and Time Point**

Dose Group	Time Point	N	Change from Baseline			
			Mean	SD	Median	Min, Max
PR Interval (msec)						
SAD Any Dose	Day 1, 4 h Post-Dose	x	x	x	x	x, x
	Day 7	x	x	x	x	x, x
	Final Visit	x	x	x	x	x, x
SAD 1 mg	Day 1, 4 h Post-Dose	x	x	x	x	x, x
	...	x	x	x	x	x, x
SAD 10 mg	Day 1, 4 h Post-Dose	x	x	x	x	x, x
	...	x	x	x	x	x, x
Placebo	Day 1, 4 h Post-Dose	x	x	x	x	x, x
	...	x	x	x	x	x, x
QRS Duration (msec)						
SAD Any Dose	Day 1, 4 h Post-Dose	x	x	x	x	x, x
	...	x	x	x	x	x, x

Note: N = Number of subjects in Safety Population with the ECG results assessed at the respective time point.

**Table 32: Summary of QTcF by Dose Group and Time Point**

[Implementation Note: For all QTcF categories that specified gender, N based on gender should be used for calculating proportions]

QTcF Category	Time Point	SAD Any Dose	SAD 1 mg	SAD 10 mg	Placebo
		n / N (%)	n / N (%)	n / N (%)	n / N (%)
QTcF >450 ms, Male	Day 1, 4 h Post-Dose	x / x (x)	x / x (x)	x / x (x)	x / x (x)
	Day 7	x / x (x)	x / x (x)	x / x (x)	x / x (x)
	Final Visit	x / x (x)	x / x (x)	x / x (x)	x / x (x)
QTcF >470 ms, Female	Day 1, 4 h Post-Dose	x / x (x)	x / x (x)	x / x (x)	x / x (x)
	...	x / x (x)	x / x (x)	x / x (x)	x / x (x)
QTcF >480 ms	Day 1, 4 h Post-Dose	x / x (x)	x / x (x)	x / x (x)	x / x (x)
	...	x / x (x)	x / x (x)	x / x (x)	x / x (x)
QTcF >500 ms	Day 1, 4 h Post-Dose	x / x (x)	x / x (x)	x / x (x)	x / x (x)
	...	x / x (x)	x / x (x)	x / x (x)	x / x (x)
30 ms ≤ QTcF increases from baseline < 60 ms	Day 1, 4 h Post-Dose	x / x (x)	x / x (x)	x / x (x)	x / x (x)
	...	x / x (x)	x / x (x)	x / x (x)	x / x (x)
QTcF increases from baseline ≥ 60 ms	Day 1, 4 h Post-Dose	x / x (x)	x / x (x)	x / x (x)	x / x (x)
	...	x / x (x)	x / x (x)	x / x (x)	x / x (x)

N= Number of subjects in Safety Population with the ECG results assessed at the respective time point. N is calculated based on specified sex for "QTcF >450 ms, Male" and "QTcF >470 ms, Female" categories.

## 14.4 Summary of Concomitant Medications

**Table 33: Number and Percentage of Subjects with Prior Medications by WHO Drug Classification and Dose Group**

[Implementation Note: Include prior medications (medications with an end date prior to first dose) only.]

WHO Drug Code Level 1, Anatomic Group	WHO Drug Code Level 2, Therapeutic Subgroup	SAD 1 mg (N=X)	SAD 10 mg (N=X)	Placebo (N=X)	All Subjects (N=X)
		n (%)	n (%)	n (%)	n (%)
Any Level 1 Codes	Any Level 2 Codes				
[ATC Level 1 - 1]	Any [ATC 1 – 1]				
	[ATC 2 - 1]				
	[ATC 2 - 2]				
	[ATC 2 - 3]				
[ATC Level 1 – 2]	[ATC 2 - 1]				
	[ATC 2 - 2]				
	[ATC 2 - 3]				

Note: N = Number of subjects in Safety Population

**Table 34: Number and Percentage of Subjects with Concomitant Medications by WHO Drug Classification and Dose Group**

[Implementation Note: Include concomitant medications (medications that are ongoing or that have an end date after first dose) only]

WHO Drug Code Level 1, Anatomic Group	WHO Drug Code Level 2, Therapeutic Subgroup	SAD 1 mg (N=X)	SAD 10 mg (N=X)	Placebo (N=X)	All Subjects (N=X)
		n (%)	n (%)	n (%)	n (%)
Any Level 1 Codes	Any Level 2 Codes				
[ATC Level 1 - 1]	Any [ATC 1 – 1]				
	[ATC 2 - 1]				
	[ATC 2 - 2]				
	[ATC 2 - 3]				
[ATC Level 1 – 2]	[ATC 2 - 1]				
	[ATC 2 - 2]				
	[ATC 2 - 3]				

Note: N = Number of subjects in Safety Population

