5.1.2 Subject Exclusion Criteria

Subjects must NOT meet any of the following exclusion criteria:

- 1) History of any hypersensitivity or allergic reaction to echinocandins or excipients (mannitol, polysorbate 80, histidine) of the rezafungin for injection and rezafungin for infusion formulations.
- 2) Subjects presenting with a clinically significant condition;⁵

⁵Subjects with any of the following must not be included into the study: clinically significant oncologic, infectious, cardiovascular, pulmonary, hepatic, gastrointestinal, hematologic, metabolic, endocrine, neurologic, immunologic, renal, psychiatric, or other condition that in the opinion of the Investigator would preclude the safe participation of the subject in the study or would prevent the subject from meeting the study requirements.

- 3) Any condition that in the opinion of the Investigator could significantly impact drug absorption, distribution, or elimination;
- 4) Symptoms of acute illness or chronic disease within 14 days of initial dosing;
- 5) Positive screen for hepatitis B virus surface antigen, hepatitis C virus antibody, or HIV antibody;
- 6) Subjects with clinical laboratory values outside the site reference ranges¹ prior to initial dosing;

¹Clinical laboratory values outside the site reference ranges, if considered by the site investigator to be clinically insignificant, are acceptable if not exceeding Grade 1 severity. One repeat of lab testing is allowed to make this determination during screening.

- 7) Abnormal ECGs. See [Section 7.1 Clinical Evaluations](#) for exceptions;
- 8) Female subject of childbearing potential who is pregnant,⁶ lactating, or planning to become pregnant during the study period or at least 30 days after the final dose of study product;

⁶Having a positive serum pregnancy test at the Screening Visit or any other specified time point prior to the dose of study product.

- 9) Received any prescription medications (except for hormonal contraceptives) within 14 days before first study drug administration;

10) Received any non-prescription medications, vitamins, herbal or dietary supplements⁷ within 14 days of initial dosing, unless prior approval is granted by both the Investigator and the Sponsor;

⁷Excluded from this list is intermittent use of acetaminophen at doses of ≤ 2 g/day or ibuprofen ≤ 1200 mg/day. However, acetaminophen only is accepted to treat AEs for pain (i.e. headaches) during in-clinic stay.

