6.4 Part 1 (Cohorts 1 through 6)

6.4.1 Day 1 – Inpatient CRU

- On the morning of Day 1, study drug or placebo will be administered via SC injection in the abdomen at a slow steady pace. Subjects will be inpatients in the CRU and will undergo the following procedures, which are listed in the Schedule of Study Procedures and Evaluations ([Appendix A](#)) and detailed in Clinical Evaluations ([Section 7](#)).
- Randomize the subject.
- Obtain vital signs before study drug dosing (within 60 minutes of study drug dosing) after resting in a supine or semi-supine position for at least 5 minutes. This is to be documented as the Baseline prior to dosing.
- Perform targeted PE.

- Obtain a 12-lead ECG after at least 5 minutes in the supine position (triplicate readings, at least 1 minute apart within a 15-minute period) and within 60 minutes before study drug dosing.
- Baseline skin assessment at SC injection site area prior to study drug dosing (see [Section 7.1.3](#) and MOP for this study).
- Administer study drug.
- Obtain vital signs at 15 minutes (± 5 min), 1 hour (± 10 min), and 2 hours (± 10 min) after dosing, after resting in a supine or semi-supine position for at least 5 minutes.
- Collect PK blood samples for pre-dose, (collected within 60 minutes before study drug dosing) and at 0.5 h (± 5 min), 1 h (± 10 min), 2 h (± 10 min), 4 h (± 10 min), 6 h (± 10 min), 8 h (± 10 min), and 12 h (± 10 min). No PK blood samples collected in Cohort 1.
- Assess reactogenicity at SC injection site(s) at 1 h (± 10 min) and 4 h (± 10 min) post-dose (see [Section 7.1.3](#) and MOP for this study).
- 12-lead ECG at 4 hours (± 10 minutes) after injection after at least 5 minutes in the supine position (triplicate readings, at least 1 minute apart within a 15-minute period).
- Assess AEs.
- Review and record any concomitant medications and non-pharmacologic treatments/procedures since admission to the CRU.
- Issue Memory Aid. Details regarding the subject Memory Aid are included in the MOP for this study.

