### **3.3.3. Study Day**

The day that the subject received study product is considered Study Day 1 for each subject. The day prior to dosing is considered Study Day = -1, not Study Day = 0.

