#### 7.1.2. Prior and Concomitant Medications

All medications will be coded using the current version of the WHO Drug dictionary. The use of prior and concomitant medications taken during the study will be summarized by Anatomical Therapeutic Code (ATC) 1 and ATC 2 (separately in [Table 33](#) for prior medications and [Table 34](#) for concomitant medications). Individual subject listings will be presented for all prior and concomitant medications (separately in [Listing 23](#) for prior medications and [Listing 24](#) for concomitant medications).

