## 16.2.10 Concomitant Medications

### Listing 23: Prior Medications

[Implementation Note: Include prior medications (medications with an end date prior to dosing) only. If start date is more than 30 days before enrollment then categorize as: 1-12 months prior to enrollment, 1-5 years prior to enrollment, or 5 years prior to enrollment.

Sort order: Dose Group, Subject ID, and CM Number.]

Dose Group	Subject ID	CM Number	Medication	Medication Start Day	Medication End Day	Indication	Taken for a condition on Medical History? (MH Description; Number)	ATC Level 1 (ATC Level 2)
SAD 1 mg	PHU.00123	001	BENADRYL	1-12 months prior to enrollment	1-12 months prior to enrollment	ITCHING	No	DERMATOLOGICALS (ANTIPRURITICS, INCL. ANTIHISTAMINES, ANESTHETICS, ETC.)

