**Listing 24: 16.2.10: Concomitant Medications**

[Implementation Note: “Medication Start Day” and “Medication End Day” are relative to enrollment (which is Day 1, day before enrollment is Day -1). For medication start dates that are > 30 days prior to enrollment, rather than use exact study days, categorize as follows:

- 5 years prior to enrollment
- 1-5 years prior to enrollment
- 1-12 months prior to enrollment

If ongoing, display “Ongoing” in the “Medication End Day” column. If taken for an AE or MH, display “Yes” with the AE or MH Number in parentheses, e.g., “Yes (RASH, 007)”. In the CSR, Subject ID should be USUBJID (not PATID) for purposes of de-identification.

Sort order: Dose Group, Subject ID, and CM Number.]

Dose Group	Subject ID	CM Number	Medication	Medication Start Day	Medication End Day	Indication	Taken for an AE? (AE Description; Number)	Taken for a condition on Medical History? (MH Description; Number)	ATC Level 1 (ATC Level 2)
SAD 1 mg	PHU.00123	001	BENADRYL	2	2	ITCHING	Yes (MACULAR RASH; 001)	No	DERMATOLOGICALS (ANTIPRURITICS, INCL. ANTIHISTAMINES, ANESTHETICS, ETC.)

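### The end-date rules for Tables 33 and 34 leave a medication that ends on the dosing day in neither table if dates are compared by calendar day

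*SAP*

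**What the plan says.** The SAP body (sections 7.1.2 and 7.9) covers the coding dictionary, the ATC levels and the table and listing numbers: "The use of prior and concomitant medications taken during the study will be summarized by Anatomical Therapeutic Code (ATC) 1 and ATC 2". It defines neither prior nor concomitant. The only definitions are in the implementation notes to the shells:

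- Table 33: "Include prior medications (medications with an end date prior to first dose) only".
- Table 34: "Include concomitant medications (medications that are ongoing or that have an end date after first dose) only".
- Listing 23: "Include prior medications (medications with an end date prior to dosing) only".
- Listing 24 (concomitant medications): no inclusion rule.

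Both medication listings show timing as a start day and an end day, with no column for clock time. On the dosing day, SAP section 3.3.3 states: "The day that the subject received study product is considered Study Day 1 for each subject".

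The protocol has medications recorded on that day. The Part 1 Day 1 procedures (section 6.4.1) include: "Review and record any concomitant medications and non-pharmacologic treatments/procedures since admission to the CRU". A footnote to the exclusion criteria (section 5.1.2) adds that "acetaminophen only is accepted to treat AEs for pain (i.e. headaches) during in-clinic stay".

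**The concern.** A prior/concomitant split should place every recorded medication in exactly one set. Here one rule takes end dates strictly before first dose and the other takes end dates strictly after it, so equality is left over. The dosing day is a day on which a short medication can plausibly occur. Subjects are inpatients, injection sites are examined at 1 h and 4 h, adverse events are assessed, and acetaminophen is permitted for pain. A single post-dose analgesic dose starts and stops on Day 1. A drug begun earlier and stopped on Day 1 is in the same position; the exclusion footnote tolerates intermittent acetaminophen or ibuprofen before dosing.

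At stake is a small undercount in a descriptive table, and possibly a concomitant-medication table that cannot be reconciled with its own listing. In groups this small, one subject is a visible share of the denominator.

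**Working it through.** The plan gives no figure to reproduce, so the check is whether the two rules together cover every case.

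**Inputs.** Let E be the medication end date and D the date of first dose (Study Day 1, SAP 3.3.3). Listing 24 counts days from enrollment rather than from dosing. In Part 1 subjects are randomized on Day 1 just before dosing (Protocol Table 11, note f), and SAP Table 2 treats enrolled and randomized as one row, so the two counts coincide.

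**Rules as written, compared by day.** Table 33: E < D. Table 34: E > D, or ongoing.

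| End of medication | Table 33 | Table 34 | Placed? |
|---|---|---|---|
| Day -1 | yes | no | once |
| Day 1 (E = D) | no | no | **not placed** |
| Day 2 or later | no | yes | once |
| Ongoing | no | yes | once |

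Listing 23 has the same strict comparison as Table 33, so it omits the Day 1 record too. Listing 24 has no rule to apply.

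**Does the SAP compare by day or by time?** The notes test an end *date*. Where the SAP displays clock time it provides a column for it: dose time in Listing 8, time of assessment in Listings 18 and 20. Neither medication listing has one. This points to day-level comparison but does not prove it, because a listing shell does not show everything that was collected.

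**Size.** Planned numbers come from Protocol Table 1 and SAP 3.3.1: 1 mg, 3; 10 mg, 6; placebo pooled over Cohorts 1 and 2, 1 + 2 = 3; all subjects, 3 + 6 + 3 = 12. Table 34 counts subjects within ATC rows, so one omitted user moves a row by at most 1/n:

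- 1 mg or placebo: 1/3 = 33 points
- 10 mg: 1/6 = 17 points
- all subjects: 1/12 = 8 points

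These are upper limits for one subject. If that subject has another qualifying medication in the same row, the row does not change.

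**After the change.** With Table 34 taking E ≥ D or ongoing, and Table 33 left at E < D, Day -1 goes to Table 33 and Day 1, Day 2 and ongoing all go to Table 34. Each case is placed once, with no overlap.

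**The case against.** The strongest reply is that the comparator in the notes is first dose, or dosing, rather than the date of first dose. Dosing is a timed event, and Listing 8 shows its time. On an ordinary reading, acetaminophen given four hours after the injection and stopped the same day did end after first dose and is concomitant. The gap opens only if both sides are reduced to calendar days. Day columns in a mock-up do not establish what the eCRF collected, and the eCRF is not among the documents. This stands as a limit on certainty: the omission is conditional. It does not remove the point, because the SAP neither states a date-time comparison nor shows a medication time that would allow one.

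A reader might also infer that same-day treatment is lost from the report altogether, or that tolerability is understated. The documents support neither:

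- Listing 24 carries no end-date restriction, and SAP 7.1.2 promises individual listings of all prior and concomitant medications. Listing 24 also links each medication to any adverse event it treated.
- Protocol section 3.3.1 assesses tolerability by solicited local reactogenicity, not by medication use. Day 1 reactions are tabulated at 1 h and 4 h in Table 11 and listed in Listing 9; unsolicited events are in Listing 10. None of these depends on Table 34.
- Where Appendix B uses non-narcotic analgesics to grade injection-site pain as moderate, it requires repeated use for more than 24 hours. Use that starts after the injection and lasts that long ends on Day 2 or later and is already in Table 34.

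**Conclusion.** The point holds in a limited form. The SAP's only definitions of prior and concomitant medication do not cover an end date equal to the dosing date. If the comparison is by calendar day, a medication that ends on Day 1 is counted in neither Table 33 nor Table 34. It may still be listed in Listing 24, in which case Table 34 and its listing would not agree.

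The consequence stays within the descriptive medication summaries. One omitted user is worth at most 33, 17 or 8 percentage points by group, under three assumptions: day-level comparison, the planned group sizes, and no other qualifying medication for that subject in the row. The SAP does not give actual Cohort 2 enrolment; with fewer subjects the possible shift would be larger. Whether any such record exists cannot be told from the documents. Severity is low. The change is worth making because SAP section 1 presents the document as sufficient for programming and requires deviations to be justified in the abbreviated CSR, so a programmer should not have to mend the rule silently.

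**What to change.** Use one pair of definitions in all four notes:

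- Table 34 and Listing 24: *ongoing, or end date on or after the date of first dose*.
- Table 33 and Listing 23: *end date before the date of first dose*.

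Add one sentence saying that a medication taken only before the injection on Day 1 will count as concomitant unless medication clock times are available to separate it.

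The cost is a few words in the shells and one changed inequality in the program. The drawback is that a drug taken only before dosing on Day 1 will be labelled concomitant, which the added sentence makes explicit.

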## 14.5 Pharmacokinetics

**Table 35: Rezafungin Concentrations in Plasma, SAD 10 mg Dose Group**

Subject ID	Nominal Time a (h)													
	0	0.5	1	2	4	6	8	12	24	48	96	144	312 (Day 14)	696 (Day 30)
PHU.00123	x	x	x	x	x	x	x	x	x	x	x	x	x	x
PHU.00124	x	x	x	x	x	x	x	x	x	x	x	x	x	x
PHU.00125	x	x	x	x	x	x	x	x	x	x	x	x	x	x
...	x	x	x	x	x	x	x	x	x	x	x	x	x	x
Statistics														
Nb	x	x	x	x	x	x	x	x	x	x	x	x	x	x
Mean	x	x	x	x	x	x	x	x	x	x	x	x	x	x
SD	x	x	x	x	x	x	x	x	x	x	x	x	x	x
GM	x	x	x	x	x	x	x	x	x	x	x	x	x	x
CV %	x	x	x	x	x	x	x	x	x	x	x	x	x	x
Min	x	x	x	x	x	x	x	x	x	x	x	x	x	x
Max	x	x	x	x	x	x	x	x	x	x	x	x	x	x

a Times are relative to time of dosing.

b Number of data points used to compute the summary statistics. For calculation of summary statistics, BQL values were imputed as 0 if they did not come after a PK sample concentration that is above the LLOQ and treated as missing otherwise.

Note: Samples that were collected substantially outside of the protocol-defined window are excluded from summary statistics (but not from NCA) and are indicated by an asterisks (\*).

**Table 36: Summary Statistics for Rezafungin PK Parameters in Plasma – SAD 10 mg Dose Group**

Statistic	PK Parameters							
	C max (ng/mL)	T max (h)	AUC 0-last (h*ng/mL)	AUC 0-inf (h*ng/mL)	λz (1/h)	t 1/2 (h)	CL/F (L/h)	V z /F (L)
N	X	X	X	X	X	X	X	X
Mean	X	X	X	X	X	X	X	X
SD	X	X	X	X	X	X	X	X
Min	X	X	X	X	X	X	X	X
Median	X	X	X	X	X	X	X	X
Max	X	X	X	X	X	X	X	X
CV %	X	X	X	X	X	X	X	X
GM	X	X	X	X	X	X	X	X

## 10.1 Disposition of Subjects

### Figure 1: CONSORT Flow Diagram

[figure not shown]
[Implementation Note: CONSORT diagram will show numbers of subjects screened and enrolled, and by Dose Group will show number randomized, treated, and completed per protocol. Additionally, it will show the number of subjects excluded from analysis populations by reason for exclusion.]

This is a place holder for Figure 1. The specifications for Figure 1 are in the implementation note.

### 14.3.1.1 Solicited Reactogenicity Symptoms

[figure not shown]
**Figure 2: Proportions of Subjects with Solicited Reactogenicity Symptoms by Dose Group and Severity**

[Implementation Note: All local reactogenicity symptoms will be listed using consistent symptom names as the solicited reactogenicity table shells, including “Any Symptoms”]

**Figure 3: Proportions of Subjects with Solicited Reactogenicity Symptoms by Dose Group, Time Point, and Severity – Any Symptoms**

[Implementation Note: Maximum severity on Day 1 will be calculated based on all time points collected on Day 1 (Day 1, 1 h Post-Dose and Day 1, 4 h Post-Dose). Maximum severity on Day 14 and Final Visit will be calculated based on records in memory aid and in clinic assessments. ]

**Figure 4: Proportions of Subjects with Solicited Reactogenicity Symptoms by Dose Group, Time Point, and Severity – Pain**

This figure will repeat Figure 3 for Pain

**Figure 5: Proportions of Subjects with Solicited Reactogenicity Symptoms by Dose Group, Time Point, and Severity – Tenderness**

This figure will repeat Figure 3 for Tenderness

**Figure 6: Proportions of Subjects with Solicited Reactogenicity Symptoms by Dose Group, Time Point, and Severity – Pruritus (Itching)**

This figure will repeat Figure 3 for Pruritus (Itching)

**Figure 7: Proportions of Subjects with Solicited Reactogenicity Symptoms by Dose Group, Time Point, and Severity – Ecchymosis (Bruising), Functional Grade**

This figure will repeat Figure 3 for Ecchymosis (Bruising), Functional Grade

**Figure 8: Proportions of Subjects with Solicited Reactogenicity Symptoms by Dose Group, Time Point, and Severity – Ecchymosis (Bruising), Measurement Grade**

This figure will repeat Figure 3 for Ecchymosis (Bruising), Measurement Grade

**Figure 9: Proportions of Subjects with Solicited Reactogenicity Symptoms by Dose Group, Time Point, and Severity – Induration (Hardness)/ Swelling, Functional Grade**

This figure will repeat Figure 3 for Induration (Hardness)/ Swelling, Functional Grade

**Figure 10: Proportions of Subjects with Solicited Reactogenicity Symptoms by Dose Group, Time Point, and Severity – Induration (Hardness)/ Swelling, Measurement Grade**

This figure will repeat Figure 3 for Induration (Hardness)/ Swelling, Measurement Grade

**Figure 11: Proportions of Subjects with Solicited Reactogenicity Symptoms by Dose Group, Time Point, and Severity – Erythema (Redness), Functional Grade**

This figure will repeat Figure 3 for Erythema (Redness), Functional Grade

**Figure 12: Proportions of Subjects with Solicited Reactogenicity Symptoms by Dose Group, Time Point, and Severity – Erythema (Redness), Measurement Grade**

This figure will repeat Figure 3 for Erythema (Redness), Measurement Grade

**Figure 13: Proportions of Subjects with Solicited Reactogenicity Symptoms by Dose Group, Time Point, and Severity – Nodule, Functional Grade**

This figure will repeat Figure 3 for Nodule, Functional Grade

**Figure 14: Proportions of Subjects with Solicited Reactogenicity Symptoms by Dose Group, Time Point, and Severity – Nodule, Measurement Grade**

This figure will repeat Figure 3 for Nodule, Measurement Grade

**Figure 15: Proportions of Subjects with Solicited Reactogenicity Symptoms by Dose Group, Time Point, and Severity – Ulceration, Functional Grade**

This figure will repeat Figure 3 for Ulceration, Functional Grade

[figure not shown]
**Figure 16: Proportions of Subjects with Solicited Reactogenicity Symptoms by Dose Group, Time Point, and Severity – Ulceration, Measurement Grade**

This figure will repeat Figure 3 for Ulceration, Measurement Grade

### 14.3.1.2 Unsolicited Adverse Events

[figure not shown]
